1.4 Sample Size Determination

1.4.1 PFS

The Randomization Phase sample size is powered based on the primary endpoint of PFS. Approximately 260 subjects will be randomized at a 1:1 ratio to the ibrutinib + venetoclax arm and the ibrutinib + placebo arm. The calculations are based on the following assumptions using EAST software Version 6.4.1:

- Target hazard ratio is 0.61, which corresponds to an improvement of 9 months in median PFS (mPFS) from 14 months to 23 months for the ibrutinib + venetoclax arm compared to the ibrutinib + placebo arm.
- A total of 134 PFS events will provide approximately 80% power at a one-sided significance level of 0.025 for the study. No interim analysis (IA) is planned for PFS.

Page 11 of 35

• Assuming an enrollment rate of approximately 10-11 subjects per month, the accrual is projected to complete approximately 21 months from the first subject in. The actual length of the study and the time to the primary analysis will depend on the actual enrollment rate and the number of events that occur.

1.4.2 OS

- Target hazard ratio is 0.65, which corresponds to an improvement of ~16 months in median OS (mOS) from 30 months to 46.2 months for the ibrutinib + venetoclax arm compared to the ibrutinib + placebo arm.
- A total of 155 OS events would provide ~76% power at a one-sided significance level of 0.025 adjusting for one interim analysis based on group sequential design with Lan-DeMets spending function with O'Brien-Fleming¹ boundary.
- It is anticipated that 112 and 155 OS events will be observed at the interim analysis (at ~40 months corresponding to the timing of the primary PFS analysis) and at the final analysis (at ~57 months), respectively. The level of significance for each analysis is described in Section 1.6.2.
- The calculation for OS is based on a log-rank test using EAST software version 6.5.

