1.5.1 Primary PFS Analysis and Interim OS Analysis

The primary PFS analysis will be conducted after approximately 150 PFS events have been observed. No interim analysis is planned for PFS.

An interim analysis (IA) is planned for OS at the time of the primary PFS analysis.

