1.6 Testing Procedure and Level of Significance

1.6.1 Adjustment of Multiplicity for Multiple Endpoints:

The one-sided Type I Family Wise Error Rate (FWER) will be controlled at 0.025 by a closed testing procedure for testing the primary endpoint (PFS) and key secondary endpoints. The following key secondary endpoints will be tested only if the primary endpoint (PFS) reaches statistical significance (1-sided 0.025) and will be ranked and tested at 1-sided statistical significance of 0.025 sequentially in the hierarchical order below:

- 1) CR rate per investigator assessment
- 2) Time to next treatment*
- 3) OS
- 4) ORR per investigator assessment

A secondary endpoint with a lower rank cannot be tested until the preceding endpoint achieves statistical significance.

*For US regulatory purposes, time to next treatment will be tested after OS as the third endpoint in the hierarchical order.

At the time of the primary PFS analysis, an interim analysis is planned for OS. Statistical significance level for each OS analysis is described in Section 1.6.2. ORR will be tested at 1-sided 0.025 using the primary PFS analysis data cut when OS significance is achieved.

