3.5 Prior and Subsequent Anti-Cancer Treatments

Anti-cancer treatment includes anti-cancer drug therapies, anti-cancer radiation, and anti-cancer transplant/immunotherapy.

Prior anti-cancer treatments are anti-cancer treatments received prior to study treatment and will be summarized using the ITT population. Subsequent anti-cancer treatments are anti-cancer treatments received after the date of the last dose of study treatment and will be summarized using the Safety Population.

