4.2 Definitions and Analyses for Efficacy Endpoints

Table 2 below describes the definitions and analyses for the efficacy endpoints.

 Table 2
 Definitions and Analyses for Efficacy Endpoints

Efficacy Endpoint	Definition	Analysis Method			
	Primary Endpoint				
PFS assessed by investigator (INV)	Time from the date of randomization to the date of the first documentation of progressive disease (PD) or the date of death due to any causes, whichever occurs first, regardless of study drug discontinuation or use of subsequent anti-cancer treatment. Post-treatment stem cell transplantation, CAR T-cell therapy, and other cellular therapies are not considered subsequent anti-cancer treatment for subjects responding to treatment (CR or PR) For the evaluation of disease progression, an adequate post-baseline assessment is defined as an assessment where there is enough evidence to indicate the subject had or had not progressed based on Cheson 2014 (Lugano Classification Criteria). In the situation where subjects did not have a baseline disease assessment or any adequate post-baseline disease assessment, they will be censored at the date of randomization.	Primary Analysis: Treatment policy strategy and composite variable strategy as listed in Section 4.1 will be implemented to address intercurrent events. Subjects without a PFS event will be censored at the date of the last adequate post-baseline disease assessment showing no evidence of disease progression. For US, additional censoring conventions will be implemented [see Sensitivity/Supplementary Analyses item 3) below]. Stratified log-rank test will be used to test the treatment effect between the two treatment arms. Stratified Cox regression model with Efron's tie handling method will be used to calculate the hazard ratio (HR) and its 2-sided 95% confidence interval (CI). In addition, Kaplan-Meier (KM) curves will be provided for both treatment arms. For each treatment arm, the 2-sided 95% Brookmeyer-Crowley confidence interval based on the log-log-transformed Greenwood variance estimate will be calculated for median PFS (mPFS); KM estimates at selected landmark points will also be provided.			

Page 23 of 35

Sensitivity/Supplementary Analyses:

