Time to next treatment (TTNT)	Time from the date of randomization to the date of the initiation of subsequent anti-cancer treatment. Post-treatment stem cell transplantation, CAR T-cell therapy, or other cellular therapies are not considered subsequent anti-cancer treatments for subjects responding to the treatment (CR or PR). Subjects without the use of subsequent anti-cancer treatment will be censored at the last follow-up date for subsequent anti-cancer therapy.	Method is the same as for the PFS analysis	
Time to worsening in FACT- Lym subscale ^{5,6}	Time from the date of randomization to the start date of worsening (defined by a ≥5 points reduction from baseline) in the Lym Subscale or death due to any cause, whichever occurs first.	Method is the same as for the PFS analysis	
	Subjects who have not met the definition of worsening will be censored at the last non-missing post-baseline PRO assessment. Subjects without baseline or post-baseline assessment will be censored at the date of randomization.		

Page 27 of 35

Efficacy Endpoint	Definition	Analysis Method			
	Exploratory Endpoints				
Progression- free Survival Based on Investigator Assessment after Initiation of Subsequent Anti-cancer Therapy (PFS2)	Time from the date of randomization to the date of the earliest of the following three types of events: • PD per investigator response assessment after administration of the first subsequent anticancer therapy • Death at any time on study • Initiation of the second subsequent anticancer therapy Subjects who did not experience a PFS2 event will be censored at the last adequate response assessment or the last follow-up for subsequent anti-cancer therapy (if they no longer have response assessments).	No inferential test will be conducted. For each treatment arm, the KM estimate of the median PFS2 (mPFS2) and the KM estimates at selected landmark points will be calculated using the same methods as for the primary PFS analysis.			

CMH: Cochran-Mantel-Haenszel; CI: confidence interval; CR: complete response; HR: estimate hazard ratio; ORR: overall response rate; OS: overall survival; PD: progressive disease; PFS: progression-free survival; PR: partial response.

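### Time to next treatment censors deaths, and the SAP lists neither a by-arm count of deaths before next therapy nor a cumulative-incidence estimate to go with the ranked test

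*SAP*

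**What the plan says.** SAP 1.6.1 places the endpoint second among the key secondaries ("2) Time to next treatment") at one-sided 0.025, after PFS and CR rate. A US footnote moves it down: "For US regulatory purposes, time to next treatment will be tested after OS as the third endpoint in the hierarchical order".

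The TTNT row of SAP 4.2, Table 2, runs from randomization to the start of subsequent anti-cancer treatment. Death is not an event; everyone else falls under the censoring rule "Subjects without the use of subsequent anti-cancer treatment will be censored at the last follow-up date for subsequent anti-cancer therapy". Protocol 10.2.3 likewise has no death component.

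The whole analysis entry for TTNT is "Method is the same as for the PFS analysis". The PFS row specifies a stratified log-rank test, a stratified Cox model, Kaplan-Meier curves and medians, and "KM estimates at selected landmark points will also be provided".

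In the same table, the FACT-Lym and PFS2 rows count death as an event. PFS and OS each have listed sensitivity or supplementary analyses; TTNT has none.

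**The concern.** A subject who dies before next therapy can never start it. Treating that death as ordinary censoring has two consequences.

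First, the TTNT hazard ratio describes next therapy alone. Its distance from the hazard ratio for next therapy or death depends on how deaths before next therapy split between the arms, so a reader needs that split.

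Second, one minus Kaplan-Meier with deaths censored is not the proportion of subjects who go on to next therapy. It is higher, and by a different amount in each arm when the arms have different hazards.

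A TTNT claim will be read as a delay in further treatment. Deaths will not be rare: in SAP 1.4.2, "It is anticipated that 112 and 155 OS events will be observed at the interim analysis" (the first number is for the interim, at about 40 months), among about 260 randomized subjects.

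**Working it through.** **1. The plan's own figures.** The documents state no event count, rate or power for TTNT, so the check starts from the OS and PFS assumptions in SAP 1.4.
- OS power, 155 deaths, HR 0.65, one-sided 0.025: Φ(½·√155·|ln 0.65| − 1.96) = Φ(0.722) = 76.5%, against about 76% stated.
- PFS power, 134 events, HR 0.61: Φ(½·√134·|ln 0.61| − 1.96) = Φ(0.901) = 81.6%, against approximately 80% stated.
- Expected deaths at T = 40 months, 130 per arm, uniform accrual over A = 21 months, exponential OS, no dropout: 130·[1 − (e^(−λ(T−A)) − e^(−λT))/(λA)] gives 63.6 (median 30) + 46.1 (median 46.2) = 109.7, against 112 stated.

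**2. Which listed outputs could show the missing count?** The quantity needed is joint: death without next therapy, by arm.

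| Output | What it leaves open |
|---|---|
| OS (SAP 4.2) | All deaths, not split by next therapy |
| PFS (SAP 4.2) | Deaths before progression; misses deaths after progression but before therapy |
| Study status and exit (SAP 3.1) | Not stated to be split by next therapy |
| Fatal TEAEs (SAP 5) | Closest, since the window closes before next therapy; but it also closes 30 days after last dose, covers treated subjects only, and admits related events at any time |
| COVID-19 and other deaths (SAP 5.1) | Split by cause only |
| Subsequent treatments (SAP 3.5) | Defined by "Subsequent anti-cancer treatments are anti-cancer treatments received after the date of the last dose of study treatment"; not crossed with death |

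**3. Kaplan-Meier against cumulative incidence.** Assumptions: a failure is next therapy or death, whichever is first; PFS stands in for it, so λ = ln 2/14 = 0.0495 per month in control and 0.61 × 0.0495 = 0.0302 in combination; a share q of failures are deaths before next therapy.
- Cumulative incidence of next therapy = (1 − q)(1 − e^(−λt))
- One minus Kaplan-Meier, deaths censored = 1 − e^(−(1−q)λt)

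Control, t = 24, q = 0.20: λt = 1.188. Cumulative incidence = 0.80 × (1 − 0.305) = 55.6%. One minus Kaplan-Meier = 1 − e^(−0.951) = 61.3%.

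Combination, q = 0.20: λt = 0.725. Cumulative incidence = 0.80 × (1 − 0.484) = 41.2%. One minus Kaplan-Meier = 1 − e^(−0.580) = 44.0%.

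| q | Control excess at 24 months | Combination excess at 24 months |
|---|---|---|
| 10% | 3.1 points | 1.5 points |
| 20% | 5.7 points | 2.8 points |
| 30% | 7.8 points | 3.7 points |

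At 20% in both arms, the difference between arms is 61.3 − 44.0 = 17.3 points by Kaplan-Meier and 55.6 − 41.2 = 14.4 points by cumulative incidence.

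**4. The hazard ratio.** With control share q0 = 0.20, combination share q1 and a failure HR of 0.61:
- TTNT HR = 0.61·(1 − q1)/(1 − q0)
- death-before-therapy HR = 0.61·q1/q0

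Setting the second to the design OS HR of 0.65 gives q1 = 0.65 × 0.20/0.61 = 0.213, and TTNT HR = 0.61 × 0.787/0.80 = 0.60.

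| q1 | Death-before-therapy HR | TTNT HR | Next-treatment-or-death HR |
|---|---|---|---|
| 10% | 0.31 | 0.69 | 0.61 |
| 20% | 0.61 | 0.61 | 0.61 |
| 30% | 0.92 | 0.53 | 0.61 |
| 40% | 1.22 | 0.46 | 0.61 |

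**5. What the count would look like.** SAP 1.5.1 says "The primary PFS analysis will be conducted after approximately 150 PFS events have been observed". Under the model, the formula in step 1 gives 86.0 control and 63.6 combination failures at 33.3 months, about 150 in all. A 20% control share is then about 17 deaths before next therapy. Combination shares of 10%, 20%, 30% and 40% are about 6, 13, 19 and 25. The listed outputs would not tell these cases apart.

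**The case against.** The strongest reply is that nothing confirmatory is wrong, and that stands. A reader might infer that censoring deaths invalidates the ranked test or inflates type I error. The documents do not support this: the log-rank test compares cause-specific hazards of next therapy validly, and SAP 1.6.1 opens TTNT only after PFS and CR rate succeed (after OS as well for the US).

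A reader might also take the 0.46 to 0.69 range in step 4 as a likely distortion. It is not. The shares are assumed, and the failure HR is held fixed, so the TTNT and death HRs must move in opposite directions. The one scenario tied to a documented figure gives 0.60. For the US, OS must first pass (SAP 1.6.2: observed HR below 0.550 at the interim, below 0.740 at an assumed 170-event final analysis), which makes an excess of early deaths on the combination much less plausible.

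The landmark point is partly inferred. The TTNT row mentions no landmarks; they come with the PFS method. The SAP does not say that one minus Kaplan-Meier will be reported as a proportion treated, and the curve misleads only if read that way. Larger gaps at 36 months are tempting to quote, but at the modelled 150-event cut the longest follow-up is about 33 months, so no such estimate would exist.

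Finally, the SAP sets out key elements and is not a full list of tables. The supportable statement is that it lists no such output, not that none will be made. PFS and fatal TEAEs do give partial context.

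**Conclusion.** The point holds as a modest gap in description and interpretation. The ranked TTNT analysis is valid, but no listed output gives deaths before next therapy by arm. Kaplan-Meier landmarks taken from the PFS method would overstate the probability of next therapy if read as such: about 3 to 8 points in control and 1.5 to 3.7 points in combination at 24 months, for assumed death shares of 10% to 30%.

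These sizes rest on exponential failure with PFS as proxy, next therapy starting at failure, and a death share that the documents do not give. That there is some overstatement needs only deaths before next therapy ahead of the landmark, which is close to certain with 112 deaths expected. A material shift in the hazard ratio would need a marked imbalance in those deaths between arms. The documents give no reason to expect one; the by-arm count would show whether it occurred.

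**What to change.** Keep the ranked definition, test and alpha. Before unblinding, the point by which SAP 1 says the SAP will be final, add to the TTNT row of Table 2:

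1. Cumulative incidence of next treatment by arm, with death before next treatment as a competing event, for landmark estimates in place of one minus Kaplan-Meier.
2. The number of deaths before next treatment by arm.
3. A supplementary analysis of time from randomization to next treatment or death from any cause, with the same stratified log-rank test and Cox model, outside the testing hierarchy.

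The cost is a few lines of text and three outputs from data already collected. The downside is slightly more analysis, and item 3 overlaps with PFS and OS. These outputs put the TTNT hazard ratio in context; they cannot show whether the deaths were related to the need for treatment.

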7.1.5 Patient-Reported Outcomes

7.1.5.1 FACT-Lym for Safety Run-in and Randomization Phase

The FACT-Lym questionnaires (Appendix I) will be administered in this study. The FACT-Lym was originally developed to assess functional status and well-being of patients with NHL (Eremenco 2004). Reliability and validity have been assessed in NHL (Webster 2005) and more recently construct validity has been supported in subjects with relapsed/refractory MCL (Carter 2008).

The FACT-Lym consists of the Functional Assessment of Chronic Illness Therapy - General (FACT-G) and a lymphoma-specific additional concerns subscale (Lym).

Responses to all items are rated on a 5-point scale ranging from 0 "not at all" to 4 "very much". The recall period is the past 7 days. The lymphoma subscale includes 15 items and scores range from 0 to 60. Two summary scores may also be calculated: the FACT-Lym total score (FACT-G plus Lym) and the FACT-Lym trial outcome index (TOI) score (physical well-being+functional

well-being+lymphoma). Higher scores represent better functional status and well-being for all subscales and summary scales.

The subscale of most interest in this study will be the Lym subscale. Carter (Carter 2008) and Cella et al. (Cella 2005) reported a minimal important change score for the Lym subscale in a relapsed/refractory MCL population range from approximately 2.9 to 5.4. Therefore, a 5-point change in the Lym subscale was selected as a conservative estimate of clinically meaningful deterioration in lymphoma symptoms. Time to complete the FACT-Lym is approximately 7 to 12 minutes. All translations not currently available will be completed according to best practice guidelines for translating PRO instruments to the local language(s) (Wild 2005).

The FACT-Lym questionnaire (Appendix I) will be administered at the beginning of the clinic visits prior to any procedures or physician interactions to prevent influencing subject perceptions. The questionnaires will be administered on Week 1 Day 1, Week 13 Day 1 (±7 days); every 4 weeks for the remainder of the first year; every 8 weeks during the second and third years; and every 12 weeks thereafter until disease progression.

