7.2.2 Survival

After progression, survival status will be assessed approximately every 12 weeks until death, withdrawal by subject, or study terminated by Sponsor, whichever comes first. Data on the subsequent lines of anticancer therapy will be captured. Survival sweeps will be conducted at the time of the final analysis. All subjects who are on study and not known to have died prior to the survival sweep will be contacted at that time.

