8.3.2 Long-term Follow-up

Subjects in Long-term Follow-up will be contacted approximately every 12 weeks (±14 days) by clinic visit or telephone to assess survival and the use of alternative anticancer therapy. Subjects will be contacted until death, subject withdrawal, or study termination by the Sponsor, whichever occurs first.

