- Risk of TLS is to be re-assessed prior to each venetoclax dose ramp-up. Administration of prophylaxes as needed is to occur within 72 hours of dosing. Subjects with high tumor burden at baseline may be hospitalized for a minimum of the first 24 hours of treatment (and up to 48 hours at the discretion of the investigator) at the start of the 20 mg (ramp-up dose) and the 50 mg dose levels and blood chemistry (creatinine, uric acid, potassium, phosphorus, calcium, and albumin, if available) should be monitored pre-dose and 4±1, 8±1, 12±1, 24±2 and as needed 48±2 hours after the venetoclax dose. Additionally, for high-risk TLS subjects, post-dose blood chemistries will be monitored at pre-dose and 6-8 hours after the venetoclax dose during ramp up of the 100 mg, 200 mg and 400 mg dose levels. For all other subjects, blood chemistry will be monitored pre-dose, 6-8 and 24±2 hours after the venetoclax dose at the 20 mg and the 50 mg dose levels.
- P PRO questionnaires (FACT-Lym, EQ-5D-5L) should be completed prior to any assessments, and before being clinically evaluated by the study nurse or physician. The questionnaires will be administered on Week 1 Day 1, Week 13 Day 1 (±7 days); every 4 weeks for the remainder of the 1st year; every 8 weeks during the 2nd and 3rd years; and every 12 weeks thereafter until disease progression.
- ^q Hematology includes complete blood count with differential and platelet counts.
- ^r Blood chemistry: Sodium, potassium, chloride, BUN, creatinine, glucose, calcium, total protein, albumin, AST, ALT, alkaline phosphatase, total bilirubin, LDH, phosphate, uric acid, urea, magnesium and bicarbonate. Serum creatinine, uric acid, potassium, phosphorus and calcium should be assessed within 72 hours prior to the 1st venetoclax dose and before each dose increase.
- ^s Urinalysis: pH, ketones, specific gravity, bilirubin, protein, blood, and glucose.
- Hepatitis C antibody, hepatitis B surface antigen and hepatitis B core antibody will be evaluated. If hepatitis B core antibody or hepatitis B surface antigen or Hepatitis C antibody is positive, then PCR to quantitate hepatitis B DNA or hepatitis C RNA must be performed. DNA PCR needs to be confirmed negative (< 29 U) prior to enrollment in subjects who are hepatitis B core antibody or hepatitis B surface antigen positive. For subjects who are hepatitis C antibody positive, hepatitis C PCR needs to be confirmed negative prior to enrollment.

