1) To address the intercurrent events of use of subsequent anticancer therapy, hypothetical strategy (subjects who received subsequent anti-cancer treatment will be censored at the last adequate post-baseline disease assessment showing no evidence of PD prior to the initiation of subsequent anti-cancer treatment) is implemented.
2) Subjects who missed two or more consecutive overall disease assessments (algorithm is described in Appendix 1) prior to the PFS event will be censored at the last adequate post-baseline disease assessment showing no evidence of PD prior to the first missed disease assessment.
3) Implement the two censoring conventions from items 1) and 2) above. This will be the primary analysis only for the US regulatory consideration.
4) Analyses listed under Primary Analysis and Sensitivity/Supplementary Analyses items 1) - 3) will be repeated for the IRC assessment.
5) To address the intercurrent events of COVID-19 deaths, hypothetical strategy (Pre-PD deaths due to COVID-19 are censored) is implemented.
6) Unstratified log-rank test and unstratified Cox regression model to calculate HR and its 2-sided 95% CI; same censoring convention as the primary analysis.
Subgroup Analysis: Hazard ratio and its 95% CI from unstratified Cox regression model for each subgroup. Same censoring convention as for the primary analysis.
For the US, additional censoring conventions as specified for the US primary PFS analysis in item 3) above will be implemented.

Efficacy Endpoint	Definition	Analysis Method			
Secondary Endpoints					

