	To support ORR, duration of response (DOR) is defined for the responders (PR or CR) as time from the date of initial response (PR or CR, whichever occurs first) to the date of first documentation of PD or death, whichever occurs first, regardless of the use of subsequent anticancer therapy. Censoring convention is the same as for the PFS primary analysis.	
	For the US, additional censoring conventions as specified for the US primary PFS analysis in item 3) under Analysis Method will be implemented for duration of response.	
Minimal Residual Disease (MRD)- Negative Remission Rate	For CR subjects per investigator only: Proportion of subjects achieving an MRD- negative remission, which is defined as undetectable MRD (i.e. less than the lower limit of detection for the assay) at documented CR in MRD-evaluable subjects (i.e. subjects with positive MRD at baseline) as assessed by flow cytometry of bone marrow aspirate (BMA) and/or peripheral blood (PB)), with requirement of a confirmation of MRD- negativity in subsequent peripheral blood samples at least 12 weeks later. Only subjects with samples collected at both baseline and post-baseline are included in the	For CR subjects who were MRD-evaluable, the MRD-negative remission rate will be calculated and tested by Fisher's Exact test for BMA and PB separately.
	baseline and post-baseline are included in the denominator when calculating the MRD remission rate. MRD samples collected after the initiation of subsequent anticancer therapy will not be used for this analysis.	

Efficacy Endpoint	Definition	Analysis Method	
Overall	Time from the date of randomization to the	Primary Analysis:	
Survival (OS)	date of death due to any cause.	Similar to the primary PFS analysis, composite variable strategy (COVID-19 deaths are considered OS events) is implemented to address the intercurrent events of COVID-19 deaths. Subjects without an OS event will be censored at the date last known alive.	
		Analysis methods are the same as the primary PFS analysis.	
		Sensitivity/ Supplemental Analyses:	
		1) Unstratified log-rank test and unstratified Cox regression model to calculate HR and its 2-sided 95% CI.	
		2) Hypothetical strategy (Subjects who died due to COVID-19 are censored at one day prior to the death date) is implemented to address the intercurrent events of COVID-19 deaths	

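### FACT-Lym time to worsening counts deaths long after the questionnaires stop, so the planned PFS and OS benefit alone can look like a symptom benefit

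*SAP*

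**What the plan says.** SAP Section 4.2 (Table 2) starts the clock at randomization. The event is a drop of 5 or more points from baseline "in the Lym Subscale or death due to any cause, whichever occurs first". The censoring rule follows: "Subjects who have not met the definition of worsening will be censored at the last non-missing post-baseline PRO assessment". The analysis-method column refers back to the PFS method and lists no supplementary analysis.

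Protocol 7.1.5.1 sets the questionnaires at Week 1, Week 13, then every 4 weeks in year 1, "every 8 weeks during the second and third years; and every 12 weeks thereafter until disease progression". The Appendix A footnote on PRO says the same: "every 8 weeks during the 2nd and 3rd years; and every 12 weeks thereafter until disease progression".

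Deaths are collected for longer. Protocol 7.2.2: "After progression, survival status will be assessed approximately every 12 weeks until death". Protocol 8.3.2 describes these contacts as made "by clinic visit or telephone to assess survival and the use of alternative anticancer therapy"; no questionnaire is mentioned.

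Protocol 2.2.2 asks whether the combination improves quality of life by FACT-Lym. The protocol's wording of the endpoint (10.2.3, 10.5.1.2.7) names no death component. SAP 1.6.1 tests CR rate, time to next treatment, OS and ORR after PFS; FACT-Lym is not in that list.

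**The concern.** A composite with death is a legitimate endpoint when both components stay under observation. Here one of them is switched off at progression. Take two subjects who progress without a 5-point drop. The one who later dies stays at risk until death and becomes an event. The one who survives is censored back at the last questionnaire. Time at risk therefore depends on a future death, and every event after progression is a death.

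The trial is designed on the assumption that venetoclax lengthens both PFS and OS. Those gains enter this endpoint even if symptoms worsen at the same rate in both arms. Because the result is labelled worsening and no breakdown is planned, a reader of the single hazard ratio could not tell a symptom effect from survival already reported under OS.

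**Working it through.** **Inputs from the documents** (SAP 1.4): 260 subjects 1:1, accrual 21 months, PFS medians 14 and 23 months, OS medians 30 and 46.2 months, primary PFS analysis at about 40 months. Questionnaire visits are as in Protocol 7.1.5.1.

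**The plan's own figures first.** Power = Φ(½·√d·|ln HR| − 1.96).
- PFS: ½·√134·0.494 − 1.96 = 0.90, so 81.6% (stated about 80%).
- OS: ½·√155·0.431 − 1.96 = 0.72, so 76.5% (stated about 76%).
- Expected deaths with uniform accrual: 110 at 40 months and 150 at 57 months (stated 112 and 155).

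The planning inputs are therefore understood correctly.

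**Assumptions not in the documents**
- Exponential times, no dropout.
- Lym worsening at the same rate in both arms, with medians of 6 to 60 months, independent of progression and death.
- A share f of PFS events are deaths (5% to 30%).
- Survival after progression has a constant hazard c chosen to return the OS medians. With a = ln 2/median PFS and b = (1 − f)a, S(t) = e^(−at) + b(e^(−at) − e^(−ct))/(c − a) is set to 0.5 at the OS median. At f = 20% this gives post-progression medians of 14.3 and 20.2 months.

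**An ordinary composite, for comparison.** If questionnaires never stopped, the hazards would add: HR = (1/W + 1/46.2)/(1/W + 1/30) for worsening median W. At W = 24 this is (0.04167 + 0.02165)/(0.04167 + 0.03333) = 0.84. At W = 6 it is 0.94, and at W = 60 it is 0.77.

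**The rule as written.** Worsening is seen only at scheduled visits up to progression, death counts at any time, and everyone else is censored at the last questionnaire. Large-sample unstratified Cox HR at 40 months, by worsening median in months:

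| Share of PFS events that are deaths | 6 | 12 | 24 | 36 | 60 |
|---|---|---|---|---|---|
| 5% | 0.98 | 0.89 | 0.78 | 0.72 | 0.65 |
| 15% | 0.98 | 0.89 | 0.78 | 0.72 | 0.66 |
| 20% | 0.98 | 0.89 | 0.79 | 0.73 | 0.67 |
| 30% | 0.97 | 0.89 | 0.79 | 0.74 | 0.68 |

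Worsening alone, censored at the last questionnaire, gives about 1.00 throughout. With death independent of progression the range from 6 to 60 months is 0.96 to 0.71. With a 57-month cut it is about 1.00 to 0.68, and with a 33-month cut (about 150 PFS events) 0.96 to 0.67.

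With 130 per arm and a 15% death share, the chance of a nominal one-sided p below 0.025 favouring venetoclax is about 3%, 11%, 34%, 49% and 69% across the five medians.

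**Where the events come from** (median 24 months, death share 20%):

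| | Worsenings | Deaths before progression | Deaths after progression | Total |
|---|---|---|---|---|
| Control | 41 | 15 | 35 | 91 |
| Venetoclax | 50 | 11 | 20 | 81 |

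The control excess of 10 is −9 + 4 + 15. Deaths after progression are 55 of 172 events, or 32%. The larger number of worsenings on venetoclax is not harm: the hazards are equal by construction, and later progression means longer questionnaire follow-up.

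**The case against.** **Slow worsening is the less likely case.** The event is a single drop with no confirmation, checked often in year 1. Measurement noise alone, with an assumed per-assessment SD of 3, would give a median time to first drop of about 11 months; at SD 4 it is about 6.7 months and at SD 2.5 about 26 months. The documents give no SD. This stands: the 60-month value is an extreme, and at 6 to 12 months the artefact is small.

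**The death component is stated in the definition, PFS and OS are reported separately, and the endpoint carries no alpha.** All true, and it limits the consequence. It does not tell a reader what share of the FACT-Lym result is death.

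**A reader might infer that the censoring sentence removes deaths**, since a subject who dies without a drop has not met the definition of worsening. That would void the death clause in the event definition. The only reading that gives both sentences effect counts deaths as events. The sentence is loosely drafted, no more.

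**A reader might also infer that the US censoring rules are left open for this endpoint.** The text does not support that. Time to next treatment carries the same cross-reference to the PFS method, and censoring at subsequent therapy would remove its own event; so the phrase must mean the test, model and curves. Where the US conventions are meant, the SAP says so, as for DOR: "additional censoring conventions as specified for the US primary PFS analysis in item 3) under Analysis Method will be implemented for duration of response". The missed-visit rule is also written for imaging: "Subjects who missed two or more consecutive overall disease assessments (algorithm is described in Appendix 1) prior to the PFS event will be censored".

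**Conclusion.** The concern holds. As written, the planned PFS and OS benefit can produce an apparent benefit in time to worsening when symptoms do not differ. The size depends on a worsening rate that the documents do not give: HR about 0.98 to 0.89 at medians of 6 to 12 months, about 0.8 at 24 months, and about 0.67 at 60 months. These move by about 0.05 with the share of PFS events that are deaths, the joint PFS and OS model, and the data cut. They assume that worsening is independent of progression and death.

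Two stronger conclusions do not follow. The composite is not invalid in itself. Nor is there type I error inflation, because SAP 1.6.1 leaves FACT-Lym outside the tested hierarchy. What is at stake is a misleading answer to the quality-of-life objective.

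**What to change.** 1. Label the endpoint *time to worsening or death*.
2. Reword the censoring sentence: *subjects with neither a 5-point reduction nor death are censored at the last non-missing PRO assessment*.
3. Tabulate by arm the worsenings, deaths before progression and deaths after progression.
4. Add one supplementary worsening-only analysis: a cause-specific HR censored at the last FACT-Lym, with cumulative incidence treating death as a competing event. Add a sensitivity analysis that does not count deaths long after the last questionnaire, for example more than two scheduled PRO visits.
5. State that no symptom claim rests on the composite alone.

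The cost is SAP wording and a few outputs, with no new data and no effect on the primary or key secondary tests.

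The additions have limits that should be stated with them. Worsening-only has fewer events (91 against 172 at a 24-month median), so wider intervals. It describes symptoms only up to progression. It is biased against the experimental arm if worsening and progression are correlated: at an assumed correlation of 0.5 and no symptom effect, the HR runs from 1.07 to 1.26 across medians of 6 to 60 months. The two-visit sensitivity reduces the artefact but does not remove it: 0.79 becomes 0.85 at a 24-month median and 0.67 becomes 0.75 at 60 months, while at 6 months it does not help (0.98 becomes 0.95). It is therefore a sensitivity analysis and not a replacement rule.
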